1.1. Schedule of Visits and Procedures

The schedule of visits and procedures can be found in the protocol in Table 3.

2. Statistical Hypotheses

In Part A, there is no formal statistical hypothesis under test.

3. Interim Analyses

The final analysis will be performed once all subjects have completed Visit 7 'end of treatment'. An analysis update will be performed once all subjects will have completed Visit 10.

In Part A, no formal interim statistical analysis will be performed. However, the snapshot analyses may be performed for each cohort once subjects within a cohort will have been followed up for at least 7 days following the dose. Snapshot analyses may be performed for younger and older dose cohorts.

A snapshot analysis is a preliminary analysis of an ongoing study based on all data collected until a pre-defined data cut-off date.

3.1. Data Monitoring Committee (DMC)

In Part A, no DMC is planned.

There will be a Safety Review Committee (SRC). For details see protocol section 10.1.5.

4. Sample Size Determination

No formal sample size calculations have been performed.

For Part A, the inclusion of 12 subjects per group is considered to be adequate for a safety assessment of vaccine per cohort. The probability to observe a particular treatment emergent adverse event (TEAE) with incidence of 15% at least once in 12 subjects per group is 85.8%.

5. Analysis Sets and Subgroups

5.1. Analysis Sets

Screened Set (SCR)

The screened set is defined as all subjects who signed informed consent.

Safety Set (SAF)

The safety set is defined as all subjects who received at least one dose of Investigational Medicinal Product (IMP).

Safety Boost Set (SAFB)

The safety boost set is defined as all subjects who received two doses of IMP (prime and boost immunization).

Immunogenicity set (IMM)

The immunogenicity set is defined as all subjects who received at least one dose of IMP and have at least one post-baseline functional antibody titer immunogenicity assessment.

Immunogenicity per-protocol set (IMMPP)

The immunogenicity per-protocol set is defined as all subjects included in the immunogenicity set that have no major protocol deviations as determined by the clinician.

Note: In all analysis sets, subjects will be assigned to the dose cohort according to the actual dose they received ("as treated").

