5.2. Protocol Deviations

Protocol deviations are failures to adhere to the inclusion/exclusion criteria and protocol requirements and will be classified into major protocol deviations and minor protocol deviations.

Major protocol deviations will be identified by medical review prior to database snapshot for main analysis.

The following criteria might be considered as major protocol deviations:

- (1) Violation of major inclusion or exclusion criteria
- (2) Assignment to incorrect dose (i.e. actual dose taken differs from the scheduled)
- (3) Non-Compliance (e.g., only one vaccine was administered or no vaccine was administered)
- (4) Intake of prohibited concomitant medication

Protocol deviations will be reported as related to COVID-19 or not.

Major and all protocol deviations will be presented in a listing. The number and percentage of subjects with major protocol deviations will be summarized in total and by protocol deviation type and by cohort.

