6.1. General Considerations

The following described statistical analyses only refer to Part A of the study.

No formal statistical testing will be done.

Unless otherwise specified, analyses will be based on data pooled across all study sites.

Data assessed after the vaccination with a non-trial vaccine will be excluded from all statistical analyses.

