6.2. Subject Dispositions

For the SCR, a listing of subjects having failed screening will be presented.

Subject disposition will be listed with date of informed consent, date of screening, date of immunization and date of study completion/discontinuation.

The number and percentage of subjects in the analysis sets will be summarized by group (i.e. by cohort) and cohort-total for the subjects in the SAF.

For the SAF, number and percentage of subjects having prematurely discontinued the study with a summary of the primary reason (e.g., adverse events, death, withdrawal by subject, lost to follow-up), of subjects who completed the end of treatment phase (merged from End of Trial variable and End of Treatment variable (each subject has only one data entry)) and who completed the follow-up phase will be presented by group (i.e. by cohort) and cohort-total.

Subjects having prematurely discontinued will be listed with date and reason for premature discontinuation.

Subjects in the SCR but excluded from SAF, subjects in SAF but excluded from SAFB/ IMM/ IMMPP will be listed with reason for exclusion.

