- Related TEAE
- Grade >=3 TEAE
- Related grade >= 3 TEAE

EudraCT No: 2020-003267-26

- TEAEs with dose limiting toxicity (DLT)
- Any treatment emergent serious adverse event (TESAE)
- Related TESAE
- Deaths

Overall summary of TEAEs

The number and percentage of subjects reporting at least one TEAE and the number of TEAEs will be summarized for all TEAE types defined above for each defined time interval.

The same analysis will be done for treatment emergent AESIs (TEAESIs) by time intervals.

The same analysis will be done excluding TEAEs which fulfil the following criteria:

- Are based on solicited reporting via subjects' diaries (all preferred terms included in 'BNT162-01 AEs based on solicited reporting via subjects diaries v3.0') and
- For prime or boost immunization, respectively, has a start and end date in the time period between dosing and
 - 1) the day of last diary entry (inclusive) or
 - 2) day 7 after dosing (inclusive)

whatever comes first.

TEAEs with missing start or end date will remain included.

For each defined time interval, the number and percentage of subjects reporting at least one TEAE will be summarized by PT nested within SOC for each of the following AE types:

Any TEAE, Related TEAE, Grade >=3 TEAE, Related grade >=3 TEAE, Any TESAE, Related TESAE, TEAEs with unresolved, fatal or unknown outcome, and any TEAE but excluding TEAEs which are based on solicited reporting via diaries as defined for the overall summary. If a SOC / PT is reported more than once for a subject, the subject will only be counted once for this SOC / PT. All TEAE summary tables will be sorted alphabetically by SOC and PT within SOC.

TEAE by grade

The number and percentage of subjects with TEAEs will be summarized by worst grade by PT nested within SOC by time interval. The worst grade will be counted if a TEAE is reported more than once by the same subject for this SOC / PT in one time interval.

AE listings

All AEs, AEs with DLT, AEs of subjects who discontinued early due to an AE and SAEs will be listed.

TEAE figures

The most frequent TEAEs excluding TEAEs which are based on solicited reporting via diaries will be presented graphically using a bar plot by time interval.

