6.5. Secondary Analyses

Hereinafter, the secondary analyses for Part A are described.

Secondary endpoints are functional antibody responses, fold increase in functional antibody titers and the number of subjects with seroconversion. All secondary analyses will be performed using the IMM and possibly additionally the IMMPP population, see section 5.1.

All secondary analysis endpoints will be summarized by group (i.e. by cohort) and all cohorts combined (cohort-total).

The functional antibody response will be assessed at the following time points:

P/B at day 1 (day of primary immunization, pre-dose), 7 ± 1 days and 21 ± 2 days after primary immunization and at 7 ± 3 days, 14 ± 3 days, 21 ± 4 days, 28 ± 4 days, 63 ± 7 days, 162 ± 9 , and 365 ± 14 days after the boost immunization.

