6.5.3. Seroconversion

Definition

Seroconversion is defined as a minimum of 4-fold increase of functional antibody response as compared to baseline.

Analysis

The number of subjects with seroconversion will be summarized by number and percentage with 95% CI for all post-baseline time points. The denominator of the percentages will be the number of subjects with data available at the respective visit.

Seroconversion data of the functional antibody titer will be listed.

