6.7.1. Compliance

IMP compliance will be summarized by group (i.e. by cohort) and cohort-total.

Drug exposure will be listed.

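### Titer summaries at visits timed from the boost use a set that requires only one dose, so prime-only titers fall into them as the SAP is written

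*SAP*

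**What the plan says.** SAP 5.1 defines the IMM as "all subjects who received at least one dose of IMP and have at least one post-baseline functional antibody titer immunogenicity assessment". Its only set that depends on the boost is the Safety Boost Set (SAFB), which is used for adverse events. SAP 6.5 states: "All secondary analyses will be performed using the IMM and possibly additionally the IMMPP population". The same section times the later titer assessments at 7, 14, 21, 28, 63, 162 and 365 days after the boost.

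SAP 6.1.1 bases tables and figures on scheduled visits and counts subjects with non-missing data. For seroconversion, SAP 6.5.3 says: "The denominator of the percentages will be the number of subjects with data available at the respective visit". One general exclusion could remove later samples (SAP 6.1): "Data assessed after the vaccination with a non-trial vaccine will be excluded from all statistical analyses".

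Protocol 1.3 (note under Table 3) and Protocol 7.1 both require subjects who do not receive the boost to complete the remaining scheduled assessments. Table 3 times Visits 5 to 10 from Visit 4, and each includes an immunogenicity blood draw.

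**The concern.** The secondary objective is the immune response after prime and boost. A titer from a subject who had only the prime is a different quantity, yet nothing in the SAP separates the two at visits after the boost. Such a subject belongs to the IMM, attends the scheduled visit, has data available, and so is counted.

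Post-boost GMT, GMFR and the seroconversion percentage would then mix two regimens, and the printed n at a visit would not show how many of each it contains. In cohorts of about 12, one or two such subjects can move a geometric mean visibly.

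**Working it through.** **Does the text lead there?**

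1. Entry to the IMM: one dose and one post-baseline titer (SAP 5.1). An unboosted subject with a Day 8 or Day 22 titer qualifies.
2. Sampling continues: Protocol 1.3 and 7.1.
3. Tabulation: scheduled visit, subjects with data (SAP 6.1.1, 6.5.3).
4. Removal: only data after a non-trial vaccine (SAP 6.1), or a missing sample. SAP 6.5 has no rule for a missed boost.
5. Per-protocol set (IMMPP): it drops subjects with major deviations. Receipt of one vaccine only is an example in SAP 5.2, under the lead-in "The following criteria might be considered as major protocol deviations". SAP 6.1.1 says the IMMPP repeat may be done if the sets differ significantly, to be decided at the DRM. SAP 6.5 says possibly.

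Step 3 combined with step 4 puts prime-only titers into the post-boost summaries. This is a consequence of the rules; the SAP does not state it outright.

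**How large could it be?**

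The plan gives no figure on this point. Its only sample-size figure, 85.8%, reproduces as 1 − 0.85^12 = 0.8578 and is not in question.

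Inputs: 12 subjects per cohort (Protocol 9.2, SAP 4). Let m be the number unboosted and sampled at the visit, and b the number boosted and sampled. Let r be the ratio of the boosted to the prime-only geometric mean titer. The documents give neither m nor r; I assume m = 1 or 2 and r = 4 to 10.

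Pooled GMT ÷ boosted-only GMT = r^(−m/(b+m)). The same factor applies to GMFR if baselines are equal.

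| b, m | r = 4 | r = 10 | GMT lower by |
|---|---|---|---|
| 12, 0 | 1 | 1 | 0% |
| 11, 1 | 4^(−1/12) = 0.891 | 10^(−1/12) = 0.825 | 10.9-17.5% |
| 10, 2 | 4^(−2/12) = 0.794 | 10^(−2/12) = 0.681 | 20.6-31.9% |

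Seroconversion in the limiting case where every boosted and no unboosted subject converts: 11/12 = 91.7% or 10/12 = 83.3%, instead of 100%.

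Protocol 7.4 allows replacement of some subjects who discontinue before Visit 3. If an unboosted subject is replaced but still sampled, then b = 12 and m = 1. The factors are 4^(−1/13) = 0.899 and 10^(−1/13) = 0.838, a reduction of 10.1-16.2%.

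**Can a reader undo it?**

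From the tables and figures, no: n is not split by boost status. From the listings, yes: titers, fold increase and seroconversion are listed (SAP 6.5.1 to 6.5.3), and drug exposure is listed too (SAP 6.7.1).

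**The case against.** The strongest reply is that an unboosted subject has no day after boost, so a careful programmer would leave the sample out. That is a possible reading, and a reader should not take it as stated that unboosted samples are included. But the scheduled-visit rule and the data-available denominator point the other way. Two programmers could therefore produce different tables from the same SAP.

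Second, the IMMPP may already remove these subjects, and the listings allow boosted-only values to be rebuilt. Both are true. The first depends on two discretionary decisions. The second leaves the reported tables and figures unchanged.

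Third, precision is low. With n = 12, the 95% CI half-width for a GMT is 10^(2.201 × SD/√12), which is 1.34-, 1.55- or 1.80-fold at an assumed log10 SD of 0.2, 0.3 or 0.4. The shift for m = 1 (1/0.891 = 1.12 to 1/0.825 = 1.21) lies inside all three. The shift for m = 2 (1/0.794 = 1.26 to 1/0.681 = 1.47) lies inside at SD 0.3 or more. This limits the importance of the point. It does not remove a shift that always acts in the same direction when prime-only titers are lower.

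Three stronger readings are tempting and not supported:

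- A reader might infer that adverse-event percentages after the boost have the same fault, because the Safety Set includes unboosted subjects. Protocol 9.4.2 prescribes the Safety Set for these events, and SAP 6.1.1 already triggers a repeat in the SAFB when the two sets differ. What remains is a wording mismatch: SAP 6.1.1 says the repeat will be done, SAP 6.4 says possibly.
- A reader might take the status table deleted in the Protocol 10.10.8 change log as evidence that boosting was uneven across doses. That text is superseded and interim. It includes a cohort with 0 of 12 boosted, which suggests that boosts were still being given.
- A reader might conclude that the comparison between doses is distorted. That needs unboosted subjects to be unevenly spread over cohorts, and the documents do not show this.

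**Conclusion.** The point holds as a minor one. The IMM definition, continued sampling and the visit-based denominators together put prime-only titers into summaries labelled as post-boost, and no binding rule takes them out. The summaries at 7 and 21 days after the prime are unaffected.

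The size is illustrative only. It rests on an assumed titer ratio of 4 to 10 and on one or two sampled unboosted subjects in a cohort of 12. Protocol 7.1 expects permanent discontinuation of the vaccine to be rare. Samples taken after a non-trial vaccine are dropped, which may reduce the number further at late visits. If every subject was boosted, nothing changes. No hypothesis is tested, so the consequence is limited to the reported estimates, intervals and figures.

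**What to change.** In SAP 5.1, add a flag for IMM subjects who received the boost. In SAP 6.5:

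- keep all IMM subjects for visits up to and including the pre-boost sample;
- for visits after the boost, summarise GMT, GMFR and seroconversion in boosted IMM subjects;
- keep the all-IMM summary of those visits as supportive;
- list unboosted subjects separately.

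Record the change in SAP 7.1. In the same edit, the statements on the SAFB repeat in SAP 6.1.1 and 6.4 can be made to agree.

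The cost is some SAP wording, one flag and one extra set of post-boost titer tables. No new data are needed, and no extra tables if all subjects were boosted. The downsides are a slightly smaller n at post-boost visits and the fact that boosted subjects are a selected group. For the second reason the all-IMM version should stay alongside.

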5.2. Protocol Deviations

Protocol deviations are failures to adhere to the inclusion/exclusion criteria and protocol requirements and will be classified into major protocol deviations and minor protocol deviations.

Major protocol deviations will be identified by medical review prior to database snapshot for main analysis.

The following criteria might be considered as major protocol deviations:

- (1) Violation of major inclusion or exclusion criteria
- (2) Assignment to incorrect dose (i.e. actual dose taken differs from the scheduled)
- (3) Non-Compliance (e.g., only one vaccine was administered or no vaccine was administered)
- (4) Intake of prohibited concomitant medication

Protocol deviations will be reported as related to COVID-19 or not.

Major and all protocol deviations will be presented in a listing. The number and percentage of subjects with major protocol deviations will be summarized in total and by protocol deviation type and by cohort.

5.3. Subgroups

In Part A, no subgroup analysis is planned. But unless otherwise specified, younger (18 to 55 years) and older (56 to 85 years) subjects will be analyzed separately.

6. Statistical Analyses

EudraCT No: 2020-003267-26

6.1. General Considerations

The following described statistical analyses only refer to Part A of the study.

No formal statistical testing will be done.

Unless otherwise specified, analyses will be based on data pooled across all study sites.

Data assessed after the vaccination with a non-trial vaccine will be excluded from all statistical analyses.

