## 9.4.5 Other safety analyses

Safety data other than AEs that will be summarized includes clinical laboratory parameters, vital signs, and ECGs. All safety analyses will be based on the Safety Set and will be summarized descriptively by group unless otherwise stated.

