		Update of reactogenicity analysis: Analysis of grade >= 3 was replaced by an analysis of worst grade.	Analysis is more adequate.

Version: Final 3.0

Table of Contents

Contents

Title Pag	ge	1
Signatui	re Page	2
Version	History	3
Table of	Contents	5
1. 1.1. 1.2. 1.1.	Introduction Objectives and Endpoints Study Design Schedule of Visits and Procedures	7
2.	Statistical Hypotheses	.12
3. 3.1.	Interim Analyses Data Monitoring Committee (DMC)	
4.	Sample Size Determination	.14
5. 5.1. 5.2. 5.3.	Analysis Sets and Subgroups Analysis Sets Protocol Deviations Subgroups	.15
6. 6.1.	Statistical Analyses	.17
6.1.1. 6.1.2. 6.1.3.	Tables and Listings Definitions and Derivations	.18
6.2. 6.3. 6.3.1.	Subject Dispositions Baseline Characteristics Demographics	.19
6.3.2. 6.3.3. 6.4.	Concomitant Medication. Medical History Primary Analyses	.20
6.4.1. 6.4.2.	Solicited local reactions	.21
6.4.3. 6.5. 6.5.1.	Adverse events Secondary Analyses Functional antibody response	.25
6.5.2. 6.5.3.	Functional antibody titers fold increase	.26
6.6. 6.7. 6.7.1.	Exploratory Analyses Further Safety Analyses Compliance	.26
6.7.1. 6.7.2. 6.7.3.	Laboratory Assessments	.27

8.	References	33
7.3.	Appendix 3: Reporting Conventions	32
7.2.	Appendix 2: List of Abbreviations	30
7.1.	Appendix 1: Changes to Protocol-Planned Analyses	30
7.	Supporting Documentation	30
6.7.5.	Further Safety data	29
6.7.4.	ECG	

1. Introduction

EudraCT No: 2020-003267-26

This document presents the statistical analysis plan (SAP) for BNT162-04, a dose-escalation phase I/II study in healthy subjects. The results of this study might be included in a regulatory submission.

This SAP describes the detailed procedures for the planned statistical analyses for protocol version 10.0, dated 12 MAY 2021 (hereinafter referred to as "the protocol"). Changes from the protocol are documented in Section 7.1 Appendix 1.

The study consists of two parts, Part A and B. All analyses of Part A except for exploratory endpoints are described in this SAP including the analysis of CRF and laboratory data. The exploratory analyses will be described in a separate biomarker SAP developed by BioNTech. Due to changes in the overall clinical development plan, Part B will no longer be conducted.

[figure not shown]
The statistical analyses described in this document will be conducted by Staburo GmbH using SAS® software version 9.4 or higher.

This study will evaluate safety, adverse events and immunogenicity assessments data.

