6.1.1. Tables and Listings

Tables

In general, data will be summarized by cohort and all cohorts combined (cohort-total). Furthermore, selected cohorts may be combined (e.g. young and older cohorts). The cohorts and cohort-total will be presented in columns.

Descriptive summary tables as well as figures will be based on scheduled visits.

Continuous variables will be summarized by group using the following descriptive statistics: number of subjects with non-missing data (n), mean, standard deviation (SD), median, minimum (min) and maximum (max).

Descriptive statistics of titer and fold increase of titer will additionally include geometric mean and its two-sided 95% confidence interval (CI). The geometric mean titer (GMT) is calculated as the mean of the logarithm of the functional antibody titers, back-transformed into the original scale. Two-sided CIs will be obtained by calculating CIs using t-distribution for the mean of the logarithmically transformed assay results and transforming the limits back to the original scale.

Geometric mean fold rise (GMFR) is calculated as the mean of the difference of logarithmically transformed assay results (post vaccination time point – pre vaccination time point) and back-transformed into the original scale. Two-sided CIs will be obtained by calculating CIs using Student's t-distribution for the mean difference of the logarithmically transformed assay results and transforming the limits back to the original scale.

Categorical variables will be summarized by group presenting absolute and relative frequencies (n and %) of subjects in each category (including the category 'missing' if applicable). Percentages will be calculated based on the number of subjects in the respective analysis set (N) as denominator if not stated differently. Percentages may be presented with exact 95% Clopper-Pearson CIs.

SDs as well as CIs will only be calculated if values of at least 3 subjects are available.

Listings

Important Case Report Form (CRF) data as well as all relevant generated and transformed variables together with the original data items will be listed. Unless otherwise specified, cohort will always be included in listings, and listings will be sorted first by cohort, then by subject

number and finally, if applicable, by visit number and/or a relevant date (e.g. date of onset of Adverse Event (AE)).

Programming

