6.4.3. Adverse events

Definition

For detailed information on adverse events see section 10.3 of the protocol.

AEs will be coded using the Version MedDRA® 23.1 including specific terms for COVID-19 to get a system organ class (SOC) and preferred term (PT) for each AE.

A TEAE is defined as any AE with an onset after the first immunization (if the AE was absent before the first immunization) or worsened after the first immunization (if the AE was present before the first immunization). AEs with an onset date more than 28 days after the last immunization will be considered as treatment emergent only if assessed as related to IMP by the investigator. AEs that cannot be determined to not be treatment emergent due to missing date or time will be defined as TEAE.

Clarification: AEs with an onset date at the date of the first immunization will only be considered as treatment emergent if the AE occurred after the first immunization.

The TEAEs will be evaluated for the following time intervals, clarifying and harmonizing the intervals defined in the protocol:

- Prime immunization up to boost immunization or day 28 (inclusive) after initial immunization (whatever comes first)
- Boost immunization up to day 28 (inclusive) after boost immunization
- All TEAEs (regardless of relationship assessment) occurring from
 - o Prime immunization up to day 28 after boost immunization (inclusive).
 - o If no boost immunization, up to 28 days (inclusive) after prime immunization All TEAEs assessed as related through visit 10.

The intervals starting or ending with an immunization, will start or end with the date and time of the immunization. TEAEs are assigned to the time intervals according to their start date and time.

Adverse events of special interest (AESI)

Enhanced respiratory disease or flu-like symptomatology not resolved after 7 days or with symptom kinetics that are inconsistent with a relationship to RNA immunization will be considered AESIs. AESIs are marked in the CRF.

Analysis

TEAEs with missing time and occurring on the day of prime immunization will be assigned to all intervals starting with the prime immunization. TEAEs with missing time and occurring on the day of the boost immunization will be assigned to all intervals including the boost immunization.

TEAEs with missing date will be assigned to all the respective intervals if it cannot be ruled out, that it belongs to a time interval.

The following TEAE types will be analyzed:

- Any TEAE

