7.1. Appendix 1: Changes to Protocol-Planned Analyses

•

- TEAEs after 28 days after last dose are included in the overall time interval ('All TEAEs assessed as related through visit 10')
- In protocol section 9.4.2 it is stated "For each injection, the number and percentage of subjects reporting at least one local reaction or systemic reaction (i.e., solicited data collected using subject diaries) will be summarized for each of the following types using the Safety Set:
 - · Any local reactions or systemic reactions
 - Grade ≥3 local reactions or systemic reactions".

However, for each injection, the number and percentage of subjects reporting at least one local reaction or systemic reaction (i.e., solicited data collected using subject diaries) will be summarized for any local or systemic reactions as well as worst type of local or systemic reaction. No summary of grade ≥3 local reactions or systemic reactions will be presented.

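### The SAP drops all data assessed after any non-trial vaccine, with no safety exception, yet counts related TEAEs by start date through Visit 10

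*SAP*

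**What the plan says.** The rule is one sentence in SAP 6.1: "Data assessed after the vaccination with a non-trial vaccine will be excluded from all statistical analyses". The SAP version history introduces it in version 3 and gives the COVID-19 pandemic as the reason. The sentence names neither a vaccine type nor a data type, and no other SAP section exempts adverse events.

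SAP 6.4.3 includes an interval for "All TEAEs assessed as related through visit 10" and states: "TEAEs are assigned to the time intervals according to their start date and time". Appendix 7.1 presents that interval as a deliberate change from the protocol: "TEAEs after 28 days after last dose are included in the overall time interval". Neither place mentions the exclusion.

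On denominators, SAP 6.1.1 sets the default: "Percentages will be calculated based on the number of subjects in the respective analysis set (N) as denominator if not stated differently". Solicited reactions get a diary-based denominator, and for seroconversion SAP 6.5.3 says: "The denominator of the percentages will be the number of subjects with data available at the respective visit". TEAEs have no rule of their own, so the default applies.

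The protocol foresees outside vaccination. Inclusion criterion 16 asks subjects to forgo other vaccines only until 28 d after the last immunization. Section 6.5 has any vaccination after the EoT Visit recorded in the CRF up to Visit 10. Section 4.4 lets subjects join other trials once they enter follow-up.

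**The concern.** The two rules meet in late follow-up and give different answers. More than 28 d after the last dose, SAP 6.4.3 treats an AE as treatment-emergent only if the investigator judged it related to the IMP. The late events at stake are therefore ones already attributed to the trial vaccine. If the 6.1 rule removes such an event, the summary table shows its subject as event-free.

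The cut point is also unclear. SAP 6.1 cuts by when data are *assessed*, while 6.4.3 works by onset. The schedule of activities records AEs since the last visit, and Visits 8, 9 and 10 are months apart (Days 85, 184 and 387). Two programmers could produce different tables from the same data.

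A lesser matter is the breadth of the trigger. Any unrelated vaccine also removes later neutralization titers, which the stated reason does not explain.

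**Working it through.** **1. The plan's own figure.** Protocol 9.2 and SAP 4 give 85.8% for seeing a TEAE of 15% incidence at least once in 12 subjects. Check: 1 − 0.85^12 = 0.8578, which agrees. The figure presumes that an event in any of the 12 would be counted.

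**2. The two rules side by side, for a related late TEAE.**

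| Onset | Recorded | SAP 6.4.3 | SAP 6.1 |
|---|---|---|---|
| before outside vaccine | before | counted | counted |
| before outside vaccine | after | counted | dropped if *assessed* means recorded |
| after outside vaccine | after | counted | dropped |

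**3. Effect on a percentage.** The denominator stays at the analysis-set N. One dropped event in a cohort of 12 gives 0/12 in place of 1/12 = 8.3%. In cohort-total it is 1/144 = 0.7%, if all 144 planned subjects were dosed.

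**4. Exposed period** (visit days from the schedule of activities, protocol 1.3).
- Two doses, nominal: boost Day 22 + 28 d = Day 50, so exposure runs over Days 51–387, or 387 − 51 + 1 = 337 d.
- Two doses with visit windows: earliest boost Day 20, + 28 d = Day 48; latest Visit 10 is Day 387 + 14 = 401. Days 49–401 are 353 d.
- One dose: Day 1 + 28 d = Day 29, so exposure starts about Day 30. These subjects still complete all assessments (protocol 7.1).
- Protocol 8.3.1 does not require AEs to be actively sought between Visits 9 and 10, although the schedule records them at Visit 10. For nominal two-dose subjects, Days 51–184 are 134 d, and 134/337 = 40% of the period.

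**5. Titers exposed.** The post-baseline points are 7 and 21 d after prime and 7, 14, 21, 28, 63, 162 and 365 d after boost, nine in all. For nominal two-dose subjects the last three are exposed (3 of 9). For one-dose subjects from Day 30, the visits on Days 36, 43, 50, 85, 184 and 387 are exposed (up to 6 of 9).

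**6. Precision lost with titers.** SAP 6.1.1 builds the GMT interval from the t-distribution on the log scale, so the limits are GMT divided and multiplied by 10^(t(0.975, n−1) × SD/√n). The documents give no SD; log10 SDs of 0.3 to 0.7 are assumed.

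| log10 SD | n = 12 | n = 11 | n = 9 |
|---|---|---|---|
| 0.3 | 1.55 | 1.59 | 1.70 |
| 0.5 | 2.08 | 2.17 | 2.42 |
| 0.7 | 2.78 | 2.95 | 3.45 |

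Regaining one subject changes little.

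**7. Illustration of lost detection.** Assume a late related TEAE with 15% cumulative incidence over the 337 d, constant hazard, 12 subjects, and k of them vaccinated elsewhere on Day d. The chance of counting at least one event is 1 − 0.85^[(12 − k) + k(d − 50)/337].

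| Vaccinated | Day 85 | Day 184 |
|---|---|---|
| none | 85.8% | 85.8% |
| 3 of 12 | 78.0% | 80.9% |
| 6 of 12 | 65.9% | 74.4% |
| 9 of 12 | 47.2% | 65.7% |
| 12 of 12 | 18.3% | 54.0% |

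The plan uses 15% only to illustrate sample size. It gives neither a late incidence nor a vaccination count, so this table shows direction and not an estimate.

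**The case against.** The best defence is that attribution after another vaccine is confounded, so limiting the summaries is a legitimate choice. AEs and SAEs are still to be listed (SAP 6.4.3), cohorts of 12 can be read line by line, and an any-vaccine cut is simple and matches the protocol's general interest in any vaccination. This stands in part. It lowers the impact and makes the vaccine-type issue secondary. It does not correct a percentage whose numerator has been cut while its denominator has not. The SAP also does not say whether the exclusion reaches the listings.

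A reader might infer more than the documents support:

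- *That the protocol's safety analysis is overridden.* Protocol 9.4.5 says: "All safety analyses will be based on the Safety Set and will be summarized descriptively by group unless otherwise stated". That section concerns safety data other than AEs and defines who is analysed. The SAP uses the same set. The protocol's AE intervals (9.4.2) all end by 28 d after boost, and the Visit 10 interval is an SAP addition. Section 9.4.5 could bear only on other late safety data, such as vital signs at Visits 8 and 9. The protocol-planned immunogenicity data affected are the late titers.
- *That the change was made silently.* The SAP says: "Changes from the protocol are documented in Section 7.1 Appendix 1". The rule is not among the entries readable there, but one bullet is blank in the text available, so its absence cannot be asserted. The version history declares the rule openly.
- *That titer loss is hidden.* The titer tables give n, and seroconversion uses subjects with data at the visit. The shrinkage shows; only its cause does not.
- *That the primary endpoints are compromised.* The 7-d and 28-d windows largely precede any permitted outside vaccination.

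**Conclusion.** The concern holds for the late safety summaries. As written, SAP 6.1 removes related TEAEs and TESAEs after any outside vaccination from an interval that the SAP itself extends to Visit 10, and it leaves open whether onset or recording date decides. One such event turns 1/12 (8.3%) into 0/12. For titers, 3 of 9 post-baseline points are exposed in nominal two-dose subjects and up to 6 of 9 in one-dose subjects. Excluding titers after a SARS-CoV-2 vaccine is reasonable. Excluding them after unrelated vaccines is unexplained but costs little precision.

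This rests on the SAP's default denominator applying to TEAEs and on subjects keeping the agreement in criterion 16. The number of outside vaccinations is not given, so the actual effect may be nil. The point should be fixed because the wording can produce a misleading table and is cheap to change.

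**What to change.** Replace the sentence in SAP 6.1 with:

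> Functional antibody data sampled after a non-trial SARS-CoV-2 vaccination are excluded from the GMT, GMFR and seroconversion summaries. Safety data are not excluded. Related TEAEs and TESAEs through Visit 10 are counted in the main rows whatever the vaccination status; those with onset date after a non-trial vaccination are also shown in a separate sub-row and flagged in listings. Events with missing onset date that cannot be placed are kept in the main rows.

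State the number of titers excluded by this rule, by cohort and visit. Record the rule in Appendix 7.1, if it is not already there, as a change to the late titer analyses planned in protocol section 3.

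The cost is SAP wording, one flag variable, sub-rows in the TEAE and TESAE tables, and one count table. Vaccination dates up to Visit 10 should already be in the CRF (protocol 6.5). The drawback is that the main rows may include events due to the outside vaccine; the sub-row makes these visible. No dose, schedule or clinical rule changes.
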